Modified Barium Swallowing Study (MBSS). MBSSs will be conducted in a routine fluoroscopy suite with a radiologist and examining SLP present. Fluoroscopy will be captured using a high-resolution imaging platform (TIMS 2000 SP DICOM System, Foresight Imaging, Chelmsford, MA). Participants will be seated upright and positioned in the lateral and anterior-posterior viewing planes. The visualization field will include the lips anteriorly, nasal cavity superiorly, cervical spinal column posteriorly, and the pharyngoesophageal segment (PES) inferiorly.^{78,79,91-93} The MBSImP, a standardized, reliable, *reproducible*, and valid approach for the execution, assessment and interpretation of the MBSS, will be used to provide measures of swallowing physiology pre- and post-intervention. The MBSImP protocol includes 12 swallowing tasks via presentations of varying bolus consistencies, bolus volumes, and presentation methods. However, consistent with the MBSImP protocol, if a patient is unable to tolerate a swallow task because of safety (aspiration) concerns, that task is not included, and the component scores associated with the missing task are given the worst (highest) score in keeping with the statistical methods inherent in the tool. Standardized ready-to-use barium contrast (Varibar® E-Z-EM, 40% w/v, Bracco Inc.) will be presented. These swallowing tasks include: thin barium (two trials of 5ml via teaspoon, one cup sip, and sequential swallows from cup), nectar barium (one trial of 5ml via teaspoon, one cup sip, and sequential swallows from cup), thin-honey barium (one trial of 5ml via teaspoon), pudding barium (one trial of 5ml via teaspoon), a solid (one-half portion of a Lorna Doone shortbread cookie coated with 3ml pudding barium), and two additional tasks presented in the anterior-posterior viewing plane (one trial each of 5ml nectar and pudding barium). Participants will be asked to maintain a neutral

posture during the drinking tasks, since alteration of posture from the upright position may affect respiratory-swallow phasing.⁹³

Respiratory-Swallow Phase Pattern Measures.

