
AcqKnowledge software used during in-clinic RST is accessible via the desktop upon logging in to the computer. Templates are pre-programmed and once opened, the software only requires the participant to select the appropriate template and click "start" for data collection to begin. In addition to remote assistance by the treating speech-language pathologist (SLP), written and video, step-by-step tutorials will be provided to the participant for at home set-up, calibration, and training. Calibration is defined as 2 minutes of at-rest breathing and will be part of the step-

Clinical Impact of Respiratory-Swallow Training on Refractory Dysphagia in OP HNC Funding
(1010498-19)

by-step guides provided to the participant. The participant must demonstrate independence in set-up and use of equipment and software within clinic under the supervision of the treating SLP prior to use at home. All signals acquired during RST sessions will be recorded on the laptop and analyzed offline.

established hierarchy of motor skill acquisition and consistent with our preliminary study,¹⁰⁰⁻¹⁰² the RST training protocol will be divided into 3 learning modules for a total of 21 goals: identification, acquisition (performance), and mastery (Figure 5). For each goal within the identification and acquisition modules, a minimum of 8 of 10 trials will be required for the goal to be met. A minimum of 9 of 10 trials will be required during the mastery module. If the participant does not meet the goal, reinstruction will be provided. Liquids will be standardized for all patients, but participants will be trained only on liquid consistencies with PAS scores ≤ 6 identified on the pre-RST MBSS.

During the Identification Module, samples from recordings of each participant's quiet breathing cycle will be printed onto 8½" x 11" cards and used to train participants to accurately identify inspiratory and expiratory phases of the respiratory cycle. Their up-going trace will represent inspiration and down-going trace will represent expiration. Participants will be instructed to identify the mid-to-late portion of the expiratory phase of the respiratory cycle (latter ½ of the expiratory phase) (Figure 5).

Clinical Impact of Respiratory-Swallow Training on Refractory Dysphagia in OP HNC Funding (1010498-19)

Figure 6. Cue cards for training participants on lung volume and phase

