Radiation Exposure. The MBSS is a videofluoroscopic examination that includes minimal exposure to radiation. Data collected during the study will be used solely for research. The amount of radiation is minimized because fluoroscopy requires no film and radiation is kept to a minimum by tight coning of the x-ray beam to include only the superior structures of the upper aerodigestive tract. A lead apron will be used to protect reproductive organs from radiation scatter in all participants. Involvement of a trained radiologist and use of dedicated fluoroscopy equipment are likely to minimize radiation exposure. The radiation of a swallow study is approximately 40 mrem of radiation for approximately 5 minutes of exposure, which is 0.8% of the annual maximum amount permitted by the Food and Drug Administration (FDA) for radioactive drug research.¹²⁵ A fluoroscopy timer will alert the examiners if and when the 5-minute time limit is met, and the study will be subsequently stopped at this point. The average duration for each participant during the MBSS, including set-up and positioning, is approximately 30 minutes. Published data from [name] lab demonstrated the standardized MBSImP protocol increases efficiency and speed for MBSS completion.¹²⁵ It takes an average of 2.89 minutes of fluoroscopy exposure (95% confidence interval (CI) of 2.80 to 2.97 minutes), which is well under the reported 3-5 minutes encountered in an upper gastrointestinal series.¹²⁵ Interpolating from the relationship Moro et al. (2006) published, the mean of 170 seconds relates to an effective dose of approximately 0.44 mSv, while the mean in the literature of 240 seconds relates to an effective dose of approximately 0.67 mSv.^{125,126} On average, the use of a standardized protocol decreased effective dose by 0.23 mSv.¹²⁵

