Aspiration. Aspiration occurs when ingested materials enter the airway below the level of the vocal folds. Because these participants have known dysphagia, there is a risk of aspiration occurring during the MBSS.¹²⁷ If the barium is aspirated, it is not expected to cause severe lung injury due to its relatively non-irritant nature. However, acute inflammation, and even death, has been reported, despite whether it was attributed to either high or low-density preparations of barium. Participation in this investigation will *not increase the risk* of aspiration. If a swallowing impairment is observed during the examination, a referral to the participant's attending physician will be made.

The risk of aspiration will be clearly stated on the informed consent and during the consenting process. Despite this potential, our collaborative speech pathology and medical teams plan to institute measures that optimize the participant's safety. These include: 1) inclusion of

Clinical Impact of Respiratory-Swallow Training on Refractory Dysphagia in OP HNC Funding (1010498-19)

participants with no history of aspiration pneumonia during the past 12 months; and 2) liquid consistencies that result in PAS scores of ≥ 7 during the baseline MBSS will not be given during intervention portion of the study.

Participants are not required to have participated in previous traditional swallowing therapy. If they have participated in traditional swallow therapy, they must be 6 months post last treatment session and still have swallow disorders.¹²⁷ Consistent with our past trial that showed no adverse events, participants will be encouraged to swallow naturally without employing any previously instructed maneuvers or strategies. If the participant cannot swallow without a maneuver or strategy and meet inclusion criteria, he/she will be excluded from the study.

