Respiratory Monitoring and Training. Respiratory monitoring and phase training will be accomplished using Inductotrace (Ambulatory Monitoring, Inc.) data.¹²⁸ There are no known risks associated with the placement of loose elastic bands (Inductobands, Ambulatory Monitoring, Inc.)¹²⁸ around participants' chests and abdomens while data are collected on a data acquisition system (BIPOAC Systems, Inc., Santa Barbara, CA, Model MP150). There is the unlikely potential, though inconsistent with our preliminary observations, that manipulation of respiratory phase surrounding the swallow may make the participant's swallowing worse, either during the intervention or the post-intervention MBSS. If there is any clinical indication that the participant is experiencing coughing or discomfort with the task, the task will be discontinued, and the participant will be excluded from further treatment. No alternative procedures or treatments are available.

Patient Perceived Effort Associated with Training. All patients will be asked to complete the NASA Task Load Index survey. This survey contains 6 task load domains and asks the participant to indicate the mental, physical and temporal demand, performance success, effort and frustrations levels associated with the training using a visual analog rating scale.

Adequacy of Protection from Risk

Recruitment and Informed Consent

Designated approved study personnel will obtain informed consent, including PI, Study Coordinator, Research SLP (speech-language pathology), and clinical SLPs. All potential participants (volunteers) will be explained the study procedures, potential risks and benefits by the consenting study personnel. All eligible participants, regardless of race, ethnic origin, or sex, will be asked to participate as long as authorization and informed consent can be obtained. Any participant may withdraw from the study at any time without penalty or prejudice for treatment.

Protection against Risk

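### The risk section denies any added risk of aspiration, while its own text and the study procedures describe added aspiration exposure

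*Combined protocol and SAP*

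**What the plan says.** The statement at issue is in Section 5.1, Potential Risks, Aspiration: "Participation in this investigation will *not increase the risk* of aspiration".

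Other text on the same risk:

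- **Aspiration, same paragraph.** "Because these participants have known dysphagia, there is a risk of aspiration occurring during the MBSS". On barium that enters the airway, it first says severe lung injury is not expected, then adds: "However, acute inflammation, and even death, has been reported".
- **Aspiration, later in the subsection.** "participants will be encouraged to swallow naturally without employing any previously instructed maneuvers or strategies".
- **Respiratory Monitoring and Training, the next risk heading.** It says that "manipulation of respiratory phase surrounding the swallow may make the" participant's swallowing worse, in training or at the MBSS that follows. It calls this unlikely and out of line with the preliminary observations.
- **Radiation Exposure.** "Data collected during the study will be used solely for research".
- **Modified Barium Swallowing Study.** "The MBSImP protocol includes 12 swallowing tasks", with a task omitted if it raises a safety concern.
- **Respiratory-Swallow Training (RST).** "participants will be trained only on liquid consistencies with PAS scores ≤ 6", as found on the pre-training MBSS.
- **Sections 5.2 and 5.4.** Five MBSSs are required, and control participants have one more before crossing over.
- **Protection against Risk, Recruitment and Informed Consent.** The risks described earlier in the section are to be stated on the consent form and in the consent discussion.

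**The concern.** A categorical denial sits in a paragraph that names the hazard and its worst reported outcome. The swallows that carry the hazard are study procedures: the protocol schedules and pays for them, and the control condition, described as standard of care, is no active treatment. A person who does not join would not have these barium tasks or training swallows on the study's account.

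What is at stake is the accuracy of the source text for consent. Section 5.1 sends the described risks to the consent form, so staff who explain aspiration have two incompatible statements to draw on: that it can happen in a study procedure, and that taking part adds no risk of it.

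**Working it through.** No power, alpha or event figure is involved. The check is a side-by-side reading plus a count of exposures.

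**1. Number of MBSSs.** Section 5.4 gives five. Section 5.5 gives the same schedule: before training, after training, and at 1, 3 and 6 months. Section 5.2 adds one for control participants.

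The payment caps in Section 5.2 ($40 per MBSS, $30 per training session) provide a cross-check. Section 5.1 plans two sessions a week for 4 weeks: 2 × 4 = 8 sessions.

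- RST first: 5 × 40 + 8 × 30 = 200 + 240 = $440, as stated.
- Control first: 6 × 40 + 8 × 30 = 240 + 240 = $480, as stated.

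**2. Barium tasks per completer, at 12 per MBSS.**

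- RST first: 5 × 12 = 60.
- Control first: 6 × 12 = 72.

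These are maxima, because tasks can be withheld for safety or refused. Training swallows come on top, and their number cannot be derived from the text.

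**3. What the count can and cannot show.** The documents give no aspiration rate per task, so no risk can be computed. As an illustration only, assume a constant rate p per task and independent tasks (unrealistic, since aspiration clusters within people). The chance of at least one aspiration over n tasks is 1 − (1 − p)^n:

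| Assumed p | n = 60 | n = 72 |
|---|---|---|
| 0.5% | 26% | 30% |
| 1% | 45% | 52% |
| 5% | 95% | 98% |

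The range is too wide to serve as an estimate. It shows only that a small rate per task would not make the exposure negligible.

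**4. Liquids used in training.** The cut-off for training is PAS 6 or below. Section 2.0, in reporting the preliminary cohort of treated patients, groups PAS 6 to 8 as aspiration. Section 5.1, Patient Sample, describes PAS 6 or below as showing no visible tracheal residue. Both could be true if material entered the airway and was cleared, but the protocol does not say so. On the Section 2.0 grouping, a liquid that was aspirated at baseline can be a training liquid.

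**5. Effect of training.** The next risk heading allows that swallowing might become worse. It does not name aspiration, and it calls the event unlikely. Unlikely is still not the same as excluded.

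**6. Comparison.** The unconditional sentence is incompatible with its own paragraph on the MBSS. It is also hard to square with the training rule, the request to set aside earlier maneuvers, and the next risk heading.

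**The case against.** The strongest reply is that the protocol limits the risk and that its pilot points to benefit.

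- Unsafe MBSS tasks are omitted, and liquids scored PAS 7 or above are not used in training.
- People with aspiration pneumonia in the past 12 months are excluded, as are those who cannot swallow without a maneuver and still meet the criteria.
- Coughing or discomfort ends the task and further treatment. Pneumonia or worsening breathing can lead to withdrawal.
- In the pilot (Section 2.0, Table 3), PAS of 3 or more fell from 78.0% to 38.3%, and Section 5.1 reports no adverse events in the past trial.

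All of this stands as mitigation, and the pilot result weighs against assuming a net increase. It does not make the denial correct. The PAS 7 rule covers the intervention portion, not the repeat MBSSs, and a fall in PAS after training says nothing about exposure at MBSSs done before training. The 78.0% and 38.3% also mix penetration with aspiration, so they do not measure aspiration risk in either direction.

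It is also fair to say that the remark about research-only use concerns the data and appears in the radiation paragraph. The case that the MBSSs are study procedures rests on the required schedule and the payments.

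Three stronger readings are tempting, but the documents do not support them.

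- *Volunteers are told there is no added risk.* The consent form is not available for this review, and Section 5.1 says the aspiration risk will be stated on it.
- *On-study aspiration or pneumonia would be dismissed as background disease because of this sentence.* No relatedness review is described. Section 6.0 requires serious adverse events to be reported without a filter on attribution.
- *Training adds 210 swallows (21 goals × 10 trials).* Some identification goals use printed breathing traces, and the breakdown by goal is in a figure not shown.

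**Conclusion.** The contradiction is real and can be checked on the page. What the documents support is added aspiration exposure of unknown size: up to 60 barium tasks per completer (72 for control participants), plus an uncounted number of training swallows, reduced by the safeguards.

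A reader might go further and infer that participation raises the net risk of aspiration. That is not shown, since no aspiration rate per task is given and the pilot figures moved in a favourable direction.

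The conclusion rests on reading the sentence as written, without an implied qualifier such as a net or long-term sense, and on treating the scheduled MBSSs as caused by participation. No endpoint or analysis is affected. The correction matters because this section supplies the risk content for consent.

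**What to change.** 1. In Section 5.1, Aspiration, delete the sentence or qualify it. The text should say that the research MBSSs and the training swallows add aspiration exposure, that its size is unknown, and that the listed safeguards are meant to limit it.
2. Reconcile the passages that bear on PAS 6 and on worsening: the grouping in Section 2.0, and in Section 5.1 the Patient Sample description, the training rule, and the two risk paragraphs (Aspiration; Respiratory Monitoring and Training). Which classification or cut-off is right is for the investigators to decide.
3. Check the consent form against the two risk paragraphs and confirm that it does not repeat the denial.

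The cost is an edit to the protocol and, if needed, to the consent form, with a slightly less favourable risk statement. Nothing changes in the sample size, visits or analysis.

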Radiation. This research study involves exposure to a small amount of radiation. As part of everyday living, everyone is exposed to naturally occurring background radiation and receives a dose of about 3.0 mSv each year.¹²⁵ The effective dose from this study is about 0.44 mSv, which is estimated from a 3-minute exposure during a videofluoroscopic study.¹²⁵ This is equal to the average radiation all Americans receive in two months from natural background radiation, such as naturally occurring radioactivity in the soil.¹²⁶ Any risk from this small amount of radiation is too small to be measured directly and is small when compared to other every day risks.

Care should be taken to reduce the influence of all possible factors not related to improved diagnostic yield according to the as low as reasonably achievable (ALARA) principle.¹²⁵ This means that the radiation exposures resulting from the practice must be reduced to the lowest level possible considering the cost of such a reduction in dose. The amount of radiation each participant will be exposed to is relatively small since the X-ray machine is only turned on while he/she swallows. Although such doses of radiation may be potentially harmful, the risks are so small that they are difficult to measure. The potential long-term risk from the radiation doses is uncertain, but the risk to each participant is estimated to be slight. The barium that allows the liquid and food to show up on X-ray is not harmful and will stay in the body only for a relatively short period of time.

Examining SLPs will wear lead-lined, radiation shielding aprons around their chest and torso. SLPs will also wear lead-lined thyroid shields. A radiation dosimeter will also be worn to measure exposure levels that are monitored by the facility. A lead apron skirt will be provided to each participant to protect his/her reproductive organs from radiation scatter.

Female participants will not be allowed to participate if they are pregnant or if there is any possibility of being pregnant.

Based on the inclusion/exclusion criteria described above, potential Veteran and non-Veteran volunteers will be asked to participate in the study only after informed consent is obtained.

Clinical Impact of Respiratory-Swallow Training on Refractory Dysphagia in OP HNC Funding
(1010498-19)

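### The 0.44 mSv given as the radiation dose of the research study is the dose of one swallow exam; completers have five or six, and no available section states the total

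*Combined protocol and SAP*

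**What the plan says.** The Radiation paragraph under Protection against Risk (section 5.1) opens with "This research study involves exposure to a small amount of radiation". It puts background at about 3.0 mSv a year and continues: "The effective dose from this study is about 0.44 mSv", "which is estimated from a 3-minute exposure during a videofluoroscopic study". It then says "This is equal to the average radiation all Americans receive in two months from natural background radiation", and adds: "Any risk from this small amount of radiation is too small to be measured directly".

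The Radiation Exposure paragraph under Potential Risks, earlier in section 5.1, gives the source of the figure: "the mean of 170 seconds relates to an effective dose of approximately 0.44 mSv". It also gives a second per-exam figure, 40 mrem, described as 0.8% of an annual FDA maximum.

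The number of exams is stated elsewhere. Patient Sample (section 5.1) requires an MBSS before RST. Section 5.5 adds one after RST and one at each of 1, 3 and 6 months. Section 5.2 adds a further MBSS for controls just before they cross over. Section 5.4, in explaining why pregnant women are excluded, says that five are required.

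**The concern.** The paragraph's subject is the research study, and the dose it gives is the dose from this study. A reader will naturally take 0.44 mSv, and the two-month comparison built on it, as the exposure a participant accepts by joining the trial. If the figure covers one exam, that reader sees one fifth (RST arm) or one sixth (control arm) of the expected research exposure. An ethics board weighing risk needs the total. Nobody can get it from this paragraph: the inputs are spread over several sections, and the one explicit count, in section 5.4, is one short for half of those randomised.

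**Working it through.** **Inputs**
- Dose of one MBSS at the mean 170 seconds: 0.44 mSv (5.1, Potential Risks).
- Second per-exam figure: 40 mrem = 0.4 mSv, given as 0.8% of the annual maximum (same place).
- Background: 3.0 mSv a year (5.1, Protection against Risk).
- Exams: before RST, after RST, and at 1, 3 and 6 months (5.1 and 5.5); one more for controls (5.2).
- Payments: $40 per MBSS and $30 per RST session, with maxima of $440 and $480 (5.2).
- RST sessions: two a week for 4 weeks = 8 (5.1).

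**Step 1. Reproduce the plan's figure.** Months of background = dose / 3.0 × 12. For one exam, 0.44 / 3.0 × 12 = 1.76 months, which rounds to the stated two. Also 170 / 60 = 2.83 minutes, which fits the stated 3-minute basis. The statement is correct as the dose of one exam.

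**Step 2. Count the exams.** RST arm: 1 + 1 + 3 = 5. Control arm: 5 + 1 = 6. The payment maxima confirm both counts:
- 5 × $40 + 8 × $30 = $440
- 6 × $40 + 8 × $30 = $480

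**Step 3. Total dose for completers** (exams × dose per exam):

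| | RST arm (5 exams) | Control arm (6 exams) |
|---|---|---|
| At 0.44 mSv per exam | 2.2 mSv | 2.64 mSv |
| Months of background | 8.8 | 10.6 |
| At 40 mrem per exam | 2.0 mSv | 2.4 mSv |
| Months of background | 8.0 | 9.6 |

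**Step 4. Share of the annual maximum.** If 40 mrem is 0.8%, the implied maximum is 40 / 0.008 = 5,000 mrem = 50 mSv.
- At 40 mrem per exam: 5 × 0.8% = 4.0% and 6 × 0.8% = 4.8%.
- At 0.44 mSv per exam: 2.2 / 50 = 4.4% and 2.64 / 50 = 5.3%.

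The two bases should not be mixed.

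**Sensitivity only.** At the 240-second literature mean quoted under Potential Risks (0.67 mSv), the totals would be 5 × 0.67 = 3.35 mSv and 6 × 0.67 = 4.02 mSv, or 13.4 and 16.1 months of background. The plan expects the shorter time.

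**The case against.** The strongest reply is that *study* here may mean the exam. The sentence names a single 3-minute exposure as its basis, and the Potential Risks text uses the word that way when it describes the 5-minute limit: "the study will be subsequently stopped at this point". On that reading both the dose and the two-month comparison are right. This part stands, so the figure cannot be called simply false. It does not remove the point. The paragraph is introduced as being about the research study, the sentence itself separates this study from the videofluoroscopic study behind the estimate, and on either reading no total appears.

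A second reply is that both factors are disclosed and a reader can multiply. They are disclosed, but the count in section 5.4 leaves out the control arm's sixth exam.

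Third, the next paragraph of the Radiation text does address risk per participant: it speaks of doses in the plural, calls the long-term risk uncertain and judges it slight. So the plan has a qualitative statement at participant level, and only the summed figure is missing.

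Two stronger inferences are tempting, and the documents do not support either.
- **That participants were told too low a dose.** The recruitment and consent text in section 5.1 points to the Potential Risks section for what the consent must state. That text is per exam and correct, and the disputed sentence lies outside it. The consent form was not available and may give the total.
- **That the reassurance about unmeasurable risk is false for the total.** Nothing in the documents shows this. Equally, nothing supports extending the reassurance to 2.2 or 2.64 mSv.

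**Conclusion.** The point holds as a correction to risk text. The stated 0.44 mSv and two months describe one MBSS. Read as the dose of the trial, they are too low by a factor of five in the RST arm and six in the control arm, no available section gives the total, and the count in section 5.4 is one short for controls. The totals assume a participant who completes every scheduled exam at the mean fluoroscopy time, with no repeat exams.

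Severity is low to modest. On those assumptions the exposure stays below one year of the quoted background in both arms. Efficacy endpoints and analyses are untouched.

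**What to change.** - **5.1, Protection against Risk, Radiation.** Write *The effective dose of each MBSS is about 0.44 mSv* and label the two-month comparison as per exam. Add the expected totals for completers: five exams, about 2.2 mSv, 8.8 months of background (RST arm); six exams, about 2.64 mSv, 10.6 months (control arm). Limit the sentence on unmeasurable risk to a single exam or delete it; do not extend it to the total.
- **5.1, Potential Risks, Radiation Exposure.** Add totals on one per-exam dose throughout: either 2.0 and 2.4 mSv (4.0% and 4.8% of the annual maximum, at 40 mrem), or 2.2 and 2.64 mSv (about 4.4% and 5.3%, at 0.44 mSv and the implied 50 mSv maximum).
- **5.4.** Write *five MBSSs (six in the control arm)*.
- **Consent form.** Check that it states the total for each arm, and add it if not.

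The cost is a few sentences of risk text and possibly a consent revision. No procedure, endpoint, eligibility rule or analysis changes. The stated exposure becomes less favourable.
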